10.1 Definitions

The following definitions will be used in the assessment of safety:

Adverse Event (AE) is any untoward or unfavorable medical occurrence in a human subject, including any abnormal sign (for example, abnormal physical exam or laboratory finding), symptom, or disease, temporally associated with the subject's participation in the research, whether or not considered related to the subject's participation in the research.

Serious Adverse Event (SAE) is any adverse event that

- (1) results in death;
- (2) is life-threatening;
- (3) results in inpatient hospitalization or prolongation of existing hospitalization;
- (4) results in a persistent or significant disability/incapacity;
- (5) results in a congenital anomaly/birth defect; or
- (6) based upon appropriate medical judgment, may jeopardize the subject's health and may require medical or surgical intervention to prevent one of the other outcomes listed in this definition (examples of such events include allergic bronchospasm requiring intensive treatment in the emergency room or at home, blood dyscrasias or convulsions that do not result in inpatient hospitalization, or the development of drug dependency or drug abuse).

*Life-threatening* means that the event places the subject at immediate risk of death from the event as it occurred.

*Unanticipated Problem* is defined as an event, experience or outcome that meets **all three** of the following criteria:

- is unexpected; AND
- is related or possibly related to participation in the research; AND
- suggests that the research places subjects or others at a greater risk of harm (including physical, psychological, economic, or social harm) than was previously known or recognized.

*Possibly related* means there is a reasonable possibility that the incident, experience, or outcome may have been caused by the procedures involved in the research

Unexpected means the nature, severity, or frequency of the event is not consistent with either:

- the known or foreseeable risk of adverse events associated with the procedures involved in the research that are described in (a) the protocol–related documents, such as the IRBapproved research protocol, any applicable investigator brochure, and the current IRBapproved informed consent document, and (b) other relevant sources of information, such as product labeling and package inserts; or
- the expected natural progression of any underlying disease, disorder, or condition of the subject(s) experiencing the adverse event and the subject's predisposing risk factor profile for the adverse event.

### 10.2 Safety Review

Both the risks listed in Section 6.1 and unknown risks will be monitored as follows:

Adverse events will be monitored from the time of study enrollment until the end of participation. Adverse events will be monitored by medical staff using the "adverse events" CRF. Adverse event monitoring will be conducted at three mid-week calls during both titration periods. Adverse events will also be assessed on the alcohol self-administration challenge days. Subjects will be given a wallet card with a 24/7 telephone number in the event that there are adverse effects which the subject would like to consult with medical staff prior to the next scheduled visit. Adverse events will be assessed if at any point in the study a subject uses this 24/7 emergency phone contact. If a subject has an ongoing SAE or unanticipated problem at the time that the subject completes all study procedures, Adverse Event assessment will continue until satisfactory resolution (either resolved or stabilized and is not expected to resolve in the near term) of the event or problem.

For each recorded AE or SAE, the study MD staff or study nurse will assess expectedness based on the known published side effect profile for pitolisant. The study MD staff or study nurse will also assess severity based on the following criteria:

Mild:	An event that is usually transient, requiring no special treatment, and does not generally interfere with the subject's daily activities.		
Moderate:	An event that interferes with usual activities of daily living, causing discomfort but poses no significant or permanent risk of harm to the		

Mild:	An event that is usually transient, requiring no special treatment, and does not generally interfere with the subject's daily activities.		
	therapeutic intervention.		
Severe:	An event that interrupts usual activities of daily living or significantly affects clinical status. The event poses a significant risk of harm to the subject and hospitalization may be required, and typically requires intensive therapeutic intervention.		
Life-threatening	An event that puts the subject into imminent risk of death without intervention		

The study MD staff or study nurse will assess AE/SAE relationship to the investigational product based on the following criteria:

Unrelated:	The subject did not receive the investigational product, the temporal sequence of the AE/SAE onset relative to administration of the investigational product is not reasonable, or there is another obvious cause of the AE/SAE.
Unlikely:	There is evidence of exposure to the investigational product or there is another more likely cause of the AE/SAE.
Possible:	There is evidence of exposure to the investigational product, the temporal sequence of the AE/SAE onset relative to administration of the investigational product is reasonable, but the AE/SAE could have been due to another equally likely cause.
Probable:	There is evidence of exposure to the investigational product, the temporal sequence of the AE/SAE onset relative to administration of the investigational product is reasonable, and the AE/SAE is more likely explained by the investigational product than by any other cause.
Definite	There is evidence of exposure to the investigational product, the temporal sequence of the AE/SAE onset relative to administration of the investigational product is reasonable, the AE/SAE is more likely explained by the investigational product than by any other cause, and the AE/SAE shows a pattern consistent with previous knowledge of the investigational product or investigational product class.

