#### 10.4 Stopping Rules

There are no interim analyses planned that would allow for a determination of futility or overwhelming benefit. Study enrollment will be suspended under the following circumstances:

1. Severe and Serious Adverse Events. Study enrollment will be suspended in the event of a single severe adverse event or a single serious adverse event if that is determined to be unexpected and at least "possibly related." If suspended, study recruitment will not continue until a determination has been made about whether the known risks of participation have changed and the Boston Medical Center IRB has made a finding that the risk/benefit ratio remains favorable given the possible newly identified risks.

2. Risk of intoxication. Subject recruitment will also be suspended if more than one subject of the first ten subjects enrolled is discontinued by the investigator due to intoxication during the alcohol self administration trial. Due to differences in alcohol tolerance, BAL is not a reliable measure of subjects potentially posing a safety risk. Medical staff will make a subjective determination of risk based on the subject's behavior. After 10 subjects have been enrolled, the trial will be suspended if there are more than 10% of subjects whose participation has been halted by the study team due to concerns about physical safety because of intoxication during the alcohol self-administration trial. If suspended for this reason, the study team will consider design changes to reduce the likelihood of this as a potential risk to study subjects. Recruitment would resume when the BU Medical Campus/Boston Medical Center IRB has made a determination that proposed changes to the study design have an acceptable risk/benefit ratio.

- 11 Data Handling and Record Keeping
- 11.1 Confidentiality

All staff will be fully trained in the procedures for protection confidential health information. To maintain subject confidentiality, study data will be coded on CRFs that are identified by a subject number only. Source records with identifying information and CRFs will be stored in double-locked space with access only by authorized staff. Data stored in the REDcap system have strong protections including file encryption and password access. Subject information will not be released without written permission. Upon approval of the study by an IRB, NIH will furnish a Certificate of Confidentiality.

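### As worded, exposure alone satisfies the *Unlikely* causality row in 10.2, so it overlaps every higher grade; whether this touches the 10.4 suspension trigger depends on a definition that 10.4 does not name

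*Combined protocol and SAP*

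**What the plan says.** Section 10.2 sets out a five-step relatedness scale and says who applies it: "The study MD staff or study nurse will assess AE/SAE relationship to the investigational product based on the following criteria". The rows turn on four things: exposure to the product, plausible timing, how the product compares with other causes, and (for the top grade) a known pattern.

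- *Unrelated*: no product received, or timing that "is not reasonable, or there is another obvious cause of the AE/SAE"; any one of these three suffices for this grade.
- *Unlikely*: "There is evidence of exposure to the investigational product or there is another more likely cause of the AE/SAE".
- *Possible*: exposure, and timing that "is reasonable, but the AE/SAE could have been due to another equally likely cause".
- *Probable*: exposure, plausible timing, and "the AE/SAE is more likely explained by the investigational product than by any other cause".
- *Definite*: the conditions of *Probable* plus a pattern consistent with what is known of the product or its class.

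Section 10.4 suspends enrollment after a single severe or serious adverse event "if that is determined to be unexpected and at least" 'possibly related'. Section 10.1 has its own entry for that term, which "means there is a reasonable possibility that the incident, experience, or outcome may have been caused by the procedures involved in the research". Section 10.4 does not say whether it uses the 10.1 entry or the 10.2 scale.

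**The concern.** A causality scale works only if an event falls into one grade, at least at the boundary where something happens. If 10.4 is read against 10.2, that boundary is the line between *Unlikely* and *Possible*, and one event is enough to decide the outcome.

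The *Unlikely* row does not hold that line. Its first limb is a condition that every higher grade also requires, and 'or' makes that limb sufficient. An assessor who applies the criteria literally could place an event with plausible timing, even one best explained by the product, in *Unlikely* and still comply with the text. At stake is whether an unexpected severe or serious event leads to the suspension and IRB review that 10.4 promises.

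**Working it through.** The plan gives no figure to reproduce here; the check is one of logic.

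**Inputs.** The five definitions in 10.2, applied as written. Each event profile has four attributes:

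- exposure: yes or no
- timing reasonable: yes or no
- strongest alternative cause relative to the product: obvious, more likely, equally likely, or less likely
- known pattern: yes or no

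This gives 2 × 2 × 4 × 2 = 32 profiles. One assumption is needed: an obvious alternative cause also counts as a more likely one.

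**As written ('or').** *Unlikely* is met if the subject was exposed, or if another cause is more likely. All 16 exposed profiles therefore meet it. For an exposed subject with reasonable timing:

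| Alternative cause | Known pattern | Grades met as written | Grades met with 'and' |
|---|---|---|---|
| Obvious | either | Unrelated, Unlikely | Unrelated, Unlikely |
| More likely | either | Unlikely | Unlikely |
| Equally likely | either | Unlikely, Possible | Possible |
| Less likely than the product | no | Unlikely, Probable | Probable |
| Less likely than the product | yes | Unlikely, Probable, Definite | Probable, Definite |

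The profiles at *Possible* or higher are the equally likely row (2, with and without a known pattern) and the two less likely rows (2), so 4 in all. All 4 also meet *Unlikely*.

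**With 'and'.** *Unlikely* now needs exposure together with a more likely cause. Of the same 4 profiles, 0 meet *Unlikely*. No profile is left without a grade: unexposed or implausibly timed events are *Unrelated*, and the table covers the rest.

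**Residual overlaps with 'and'.** Six profiles meet both *Unrelated* and *Unlikely*, all in exposed subjects: obvious cause with reasonable timing (2), obvious cause with unreasonable timing (2), and more likely cause with unreasonable timing (2). Both grades lie below the trigger, so suspension is unaffected. *Definite* is nested in *Probable*, and both lie above it.

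**Link to 10.4.** There are two readings.

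1. 'Possibly related' means *Possible* or higher on the 10.2 scale. An event graded *Unlikely* then does not trigger suspension, and the overlap matters.
2. 'Possibly related' means the 10.1 entry. The test is then a reasonable possibility of causation by the research procedures, which a 10.2 grade of *Unlikely* does not settle.

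The two standards also differ in scope: 10.1 speaks of research procedures, 10.2 of the investigational product only. They cannot be treated as interchangeable.

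**The case against.** A reader might infer that every adverse event in a dosed subject will be graded *Unlikely* and that the suspension rule is therefore disabled. The documents do not support that, for four reasons.

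First, 10.1 says its definitions govern the safety assessment, and it defines the very term that 10.4 puts in quotation marks; the 10.2 label is *Possible*, not 'possibly related'. On that reading the trigger stands independently of the faulty row. The counter-argument is that 'at least' suggests a graded scale, and 10.2 holds the only full one. But the definition of an unanticipated problem in 10.1 distinguishes related from possibly related, and 'at least' would fit that pair as well. The question stays open.

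Second, the assessors are medical and nursing staff using an ordered scale. The neighbouring rows show the intended ladder, from an obvious other cause down to one less likely than the product. Many assessors would read 'or' as 'and', and few would call an event *Unlikely* merely because the drug was taken.

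Third, only events that are unexpected and either severe or serious can reach the trigger at all.

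Fourth, 10.1 and 10.3 give a separate route: an unanticipated problem goes to the IRB within 7 days. That route does not itself suspend enrollment, but such an event need not go unnoticed.

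These points limit the consequence. They do not cure the wording: nothing in 10.2 to 10.4 says which grade prevails when two fit, and the sense of the row has to be supplied by the assessor.

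**Conclusion.** The *Unlikely* row is wrong as written. Taken literally it is met by exposure alone and overlaps *Possible*, *Probable* and *Definite* in 4 of 4 profiles, with no tie-break. This follows from the text and rests on no outside assumption.

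The effect on enrollment suspension is conditional. It arises only if 10.4 refers to the 10.2 scale, and only if an assessor applies the row literally to an unexpected severe or serious event. If 10.4 uses the 10.1 definition, such an event could still trigger suspension. The documents give no basis for estimating how often a misgrading would occur.

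The point is minor. It is a drafting error in an operative safety rule and does not affect the sample size, the randomization or the primary analysis.

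**What to change.** 1. In the *Unlikely* row of 10.2, replace 'or' with 'and' (or 'but'), so that the grade requires exposure together with another, more likely cause.
2. In 10.4, state whether 'possibly related' means the 10.1 definition or the 10.2 scale, and reconcile the two, including their difference in scope. Which of them should govern suspension is for the sponsor and investigator to decide; the documents do not settle it.

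The overlap of *Unlikely* with *Unrelated* can stay, since neither grade reaches the trigger.

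The cost is one word in a table and one clarifying clause in 10.4, with no change to data collection or analysis. If any events have already been graded *Unlikely*, they should be re-read against the corrected row.

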#### 10.3 Reporting Plans

The Principal Investigator at BMC/BU Medical Campus will report Unanticipated Problems and Adverse Events to the BMC/BU Medical Center IRB in accordance with IRB policies:

- Unanticipated Problems occurring at BMC/BU Medical Campus will be reported to the IRB within 7 days of the investigator learning of the event.
- Adverse Events (including Serious Adverse Events) will be reported in summary at the time of continuing review, along with a statement that the pattern of adverse events, in

total, does not suggest that the research places subjects or others at a greater risk of harm than was previously known.

#### 10.4 Stopping Rules

There are no interim analyses planned that would allow for a determination of futility or overwhelming benefit. Study enrollment will be suspended under the following circumstances:

1. Severe and Serious Adverse Events. Study enrollment will be suspended in the event of a single severe adverse event or a single serious adverse event if that is determined to be unexpected and at least "possibly related." If suspended, study recruitment will not continue until a determination has been made about whether the known risks of participation have changed and the Boston Medical Center IRB has made a finding that the risk/benefit ratio remains favorable given the possible newly identified risks.

2. Risk of intoxication. Subject recruitment will also be suspended if more than one subject of the first ten subjects enrolled is discontinued by the investigator due to intoxication during the alcohol self administration trial. Due to differences in alcohol tolerance, BAL is not a reliable measure of subjects potentially posing a safety risk. Medical staff will make a subjective determination of risk based on the subject's behavior. After 10 subjects have been enrolled, the trial will be suspended if there are more than 10% of subjects whose participation has been halted by the study team due to concerns about physical safety because of intoxication during the alcohol self-administration trial. If suspended for this reason, the study team will consider design changes to reduce the likelihood of this as a potential risk to study subjects. Recruitment would resume when the BU Medical Campus/Boston Medical Center IRB has made a determination that proposed changes to the study design have an acceptable risk/benefit ratio.

- 11 Data Handling and Record Keeping
- 11.1 Confidentiality

All staff will be fully trained in the procedures for protection confidential health information. To maintain subject confidentiality, study data will be coded on CRFs that are identified by a subject number only. Source records with identifying information and CRFs will be stored in double-locked space with access only by authorized staff. Data stored in the REDcap system have strong protections including file encryption and password access. Subject information will not be released without written permission. Upon approval of the study by an IRB, NIH will furnish a Certificate of Confidentiality.

Deidentified data from this study will be submitted to the NIAAA Data archive (https://nda.nih.gov/).

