#### Risk of overconsumption

To minimize the risk of subjects reaching a level of intoxication that is uncomfortable to them, we will remind subjects that they may discontinue study participation at any time. Subjects will be asked to drink to a target BAL (0.03 g/dl) that is customary for them given the minimum drinking criteria. The alcohol self-administration paradigm that we have chosen does not include any coercion, inducements, or pressure to consume more alcohol than subjects feel comfortable consuming. There are no experimental manipulations that would increase drinking (e.g., heavy drinking confederate, anxiety manipulation). In fact, in this study design there are inducements for subjects to not drink beyond the initial priming dose. Subjects will receive monetary incentives for each drink that they do not consume. Access to medical backup services will be maintained throughout each alcohol challenge session. Subjects will be monitored during the course of the study, both through direct assessment with study staff and by observation through a video camera. Medical staff will evaluate subjects and may make a determination to halt study participation if the subject becomes too behaviorally impaired or if there are emergent safety issues. Subjects who have a BAL greater than 0.04 g/dl or who appear to be too behaviorally impaired to leave our research center will be asked to remain in the clinic until their intoxication is reduced to a level that it is safe to discharge them from the research laboratory. BAL readings will be taken twice to confirm BAL is not greater than 0.04 g/dl prior to release. Subjects will

Pitolisant effects on alcohol self administration and craving in heavy drinkers Version 1.10 7.7.2022 not be released within 60 minutes of their last drink consumed to ensure that peak BAC has been reached prior to discharge. During the descending BAL period, subjects will have access to a comfortable space with entertainment (streaming media), snacks, non-alcoholic beverages, and a nearby bathroom.

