### Medication Visit #2

After the 7-14 day washout period subjects will return to the lab to receive study medication prior to the alcohol challenge #2. Subjects will complete the same tests and interviews completed during the randomization visit (See appendix A for schedule of events). Based on the assessments at medication visit #2, subjects be discontinued for the following reasons: pregnancy, recreational drug use except for marijuana, evidence of non-compliance with study medication, suicidal thoughts or behavior, and use of a new medication that would make participation unsafe. Subjects will receive a 12-day supply of study medication and will be scheduled for the alcohol challenge #2. Subjects will be allowed to delay start of medication for up to 7 days after randomization in order to accommodate scheduling for the alcohol challenge trial.

Alcohol Challenge Trials 1 & 2: Subjects will return to the laboratory on day 12 of drug exposure for each medication trial to complete the alcohol challenge. For safety reasons, subjects will be asked to arrange transportation plans (no driving) prior each of the alcohol challenge trials. There will be a 7-14 day washout period between alcohol challenge Trial 1 and medication visit #2. The washout may extend to 14 days to accommodate the scheduling of the medication visit. Concomitant medications, urine drug screening, urine pregnancy testing, blood alcohol level will be assessed to determine eligibility to proceed with the challenge. Blood alcohol level must be 0.000 to continue with the study procedures. Urine collected for drug screening will be exposed to ultraviolet light as an objective test of medication compliance. If no fluorescence is observed in the urine sample the subject will be excluded from continuing with the challenge. Measures of drinking (TLFB) and cravings (OCDS, VAS and AUQ) will be collected to inform secondary outcomes. Subjects will be observed taking the morning dose of pitolisant (or placebo) on the day of the challenge (after compliance is confirmed via a urine screening). The peak plasma concentration of pitolisant should be reached approximately 60 minutes after administration. The alcohol self-administration session will begin no sooner than one hour after the administration of the observed 17.8 mg morning dose. The alcohol selfadministration will be conducted in the GCRU. The room will be a carpeted and furnished with

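### Rule 1 and the first-ten limb of rule 2 in Section 10.4 suspend only enrollment or recruitment, so read literally they place no study-level hold on dispensing, dosing or alcohol challenges for subjects already randomized

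*Combined protocol and SAP*

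**What the plan says.** Section 10.4 (Stopping Rules) names three different objects of suspension.

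- **Lead-in:** "Study enrollment will be suspended under the following circumstances".
- **Rule 1**, one severe or serious adverse event judged unexpected and at least possibly related: enrollment is suspended. The restart condition is "If suspended, study recruitment will not continue until a determination has been made about whether the known risks of participation have changed", together with an IRB finding that risk against benefit is still acceptable.
- **Rule 2, first ten subjects:** "Subject recruitment will also be suspended if more than one subject of the first ten subjects enrolled is discontinued" by the investigator for intoxication in the session.
- **Rule 2, after ten subjects:** "After 10 subjects have been enrolled, the trial will be suspended if there are more than 10% of subjects" halted for intoxication. The restart sentence reads "Recruitment would resume when the BU Medical Campus/Boston Medical Center IRB has made a determination" on the proposed design changes.

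The two checkpoints that a randomized subject still has to pass are in Section 9. At second-period dispensing, "Based on the assessments at medication visit #2, subjects be discontinued for the following reasons: pregnancy, recreational drug use except for marijuana"; the list goes on to non-compliance, suicidality and unsafe new medication. Before a session, "Concomitant medications, urine drug screening, urine pregnancy testing, blood alcohol level will be assessed to determine eligibility to proceed with the challenge". Neither list refers to a suspension under Section 10.4.

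**The concern.** Both triggers arise in people who are taking study medication or drinking in a session. The review under rule 1 asks whether the risks of taking part have changed, and current subjects bear those risks. Yet the action that rule 1 and the first-ten limb prescribe reaches only people who have not yet entered.

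A subject randomized just before a trigger may still have two 12-day courses and two challenges ahead. Each challenge offers eight drinks after the priming dose, and Section 9 anticipates a BAC of 0.09 to 0.13 g/dl if all are drunk. Section 6.2 states that subjects gain no direct benefit, so a pause would withhold no treatment from them.

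Staff may have to apply these rules at short notice. With three different objects in one section, two careful readers could act differently.

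**Working it through.** **Text check.** The plan gives no figure to reproduce for this point. The question is whether anything outside Section 10.4 stops exposure in one subject because of an event in another.

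| Place | What it provides | Study-level hold? |
|---|---|---|
| 6.1, Risks of study medication | Management of a subject's own reported adverse effects, including stopping the dose | No, individual |
| 6.1, Risk of overconsumption | Medical staff "may make a determination to halt study participation if the subject becomes too behaviorally impaired or if there are emergent safety issues" | No, discretionary |
| 9, Medication Visit #2 and pre-challenge checks | Individual criteria | No |
| 10.3, Reporting Plans | Unanticipated Problems go to the IRB within 7 days; adverse events are summarized at continuing review | No, reporting only |

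None is an automatic hold.

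**How many subjects are affected.** Inputs: 36 randomized and 15-20% non-completion (Section 12.2); Trial 1 is 12 to 19 days after randomization, washout is 7 to 14 days, and Trial 2 is 12 to 19 days after dispensing (Section 9). Assumption: even randomization over 24 months (730 days), which the plan gives as total study duration. A 12-month accrual (365 days) is the sensitivity case.

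- Time from randomization to Trial 2: 12 + 7 + 12 = 31 days to 19 + 14 + 19 = 52 days.
- In progress at a trigger: 36/730 × 31 = 1.53 to 36/730 × 52 = 2.56. Over 365 days: 3.06 to 5.13.
- On study medication: 36/730 × 24 = 1.18. Each subject takes pitolisant in one of the two periods, so 36/730 × 12 = 0.59 are on pitolisant. Over 365 days: 2.37 and 1.18.
- Sessions left, pitolisant and placebo together (two before Trial 1, one after it), × 0.8 for non-completion: 36/730 × (2×12 + 19) × 0.8 = 1.70 to 36/730 × (2×19 + 33) × 0.8 = 2.80. Over 365 days: 3.39 to 5.60.
- Sessions within the 7-day reporting limit: 36/730 × 2 × 7 = 0.69, or 0.55 after × 0.8. Over 365 days: 1.38 and 1.10. The plan does not say how long the IRB review would take.

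**How likely is a trigger?** The plan gives no event rates, so these are assumed.

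| Halt rate for intoxication | At least 2 of 10, all reach a session | At least 2 of 5 |
|---|---|---|
| 2% | 0.016 | 0.004 |
| 5% | 0.086 | 0.023 |
| 10% | 0.264 | 0.081 |

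The last column applies if *enrolled* means consented: Section 12.2 expects about 50% screening exclusion, so about five of ten would reach a session.

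Rule 1, at least one qualifying event in 36: 1 − 0.995^36 = 0.165 and 1 − 0.99^36 = 0.304. Multiplied by the sessions in 7 days: 0.165 × 0.55 = 0.09 to 0.304 × 0.69 = 0.21 expected sessions per trial.

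**What a hold would cost.** Paired completers lost if every subject in progress loses the pair: 1.53 × 0.8 = 1.22 to 2.56 × 0.8 = 2.05. Over 365 days: 2.45 to 4.10. Paired t-test power (noncentral t, effect size 0.7, two-sided alpha 0.01) is 0.815 at 28 completers, which agrees with the stated 0.81. It is 0.796 at 27, 0.775 at 26 and 0.727 at 24. Expected completers from 36 are 36 × 0.80 = 28.8 to 36 × 0.85 = 30.6.

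**The case against.** The strongest reply is that this is loose drafting. Under one heading the section uses enrollment, recruitment and the trial almost interchangeably, and the after-ten limb suspends the trial but restarts recruitment. That may be so, and a reader who infers that the sponsor means current subjects to continue regardless goes further than the text. The documents show an undefined scope. They do not show a decision to keep exposing people.

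A second reply is that current subjects are well watched: three adverse-event calls per dosing period, adverse-event and suicidality checks at the visits, video observation and medical backup in the session, and unblinding for medical decisions. The IRB and study-team reviews in Section 10.4 are not confined to future subjects either. This stands, and it rules out the inference that randomized subjects are unprotected. But these measures are individual, discretionary or reporting steps, and none requires a pause in others.

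Third, intoxication depends on individual tolerance, every session is supervised, and two halted sessions show that the stop authority works. This weakens the case for the first-ten limb. It also means that an intoxication trigger gives no ground for ordering everyone off study medication, since it says nothing about drug toxicity.

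Fourth, the size is easy to overstate. Someone might take the 1.2 subjects on study medication as all exposed to pitolisant, but about half are on placebo. The first-ten probabilities assume that all ten enrolled subjects reach a session. Both corrections are accepted.

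**Conclusion.** The point holds for rule 1 and the first-ten limb of rule 2. As written, neither places a study-level hold on second-period dispensing, dosing or challenges for subjects already randomized. The after-ten limb does suspend the trial, though its restart wording leaves the scope unclear.

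The effect is small and conditional on a trigger: about 1.5 to 2.6 subjects in progress, or 3.1 to 5.1 if accrual takes 12 months. The first-ten trigger probability is about 0.02 to 0.26 at assumed halt rates of 2% to 10% if all ten reach a session, and lower if enrollment means consent. The rule 1 probability is 0.17 to 0.30 at assumed event rates of 0.5% to 1%. All of these rest on even accrual and on rates that the plan does not give.

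This is a cheap improvement in subject safety. It does not affect the validity of the analysis, and investigators or the IRB could stop exposure in practice without it.

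**What to change.** Use one object in every limb of Section 10.4, for example:

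> On any trigger the trial is suspended: until the IRB finding, no subject is randomized, no study medication is dispensed (including at medication visit #2) and no alcohol challenge is run. After a rule 1 trigger, a study physician promptly reviews each subject currently on study medication and documents whether dosing stops or continues.

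In both restart sentences, replace *recruitment* with *the trial*. No default order to stop study medication after an intoxication trigger is needed, and no new provision for replacing subjects. If the sponsor does intend current subjects to continue, Section 10.4 should say so and give the reason.

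The cost is a short amendment. Data are lost only if a rule fires: about one or two paired completers, or two to four with 12-month accrual. If that leaves 26 completers rather than 28, power falls from about 0.81 to 0.77; with 24 it is 0.73. The 28.8 to 30.6 completers expected from 36 randomized absorb part of this.
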